12.4 Appendix 4: Administration-related reactions

The NCI-CTCAE distinguishes between hypersensitivity reactions and acute infusion reactions induced by cytokine release. Despite the different possible mechanisms underlying hypersensitivity and infusion reactions, the clinical signs and symptoms associated with these reactions overlap.

Immediate systemic reactions, infusion-related reactions and hypersensitivity reactions, at administration of nivolumab can be considered to be common [90, 91]. Systemic reaction at administration of EO2040 cannot be excluded either, even if not reported in the early development of the similar compound EO2401 (see [Section 1.3.2](#)).

NOTE: At administration of the treatment compounds of this trial, immediate treatment of severe allergic reactions should be available, including staff well trained in resuscitation, IV access for administration of fluids, antihistamines, corticosteroids, and epinephrine (adrenaline).

Treatment of administration-related reactions

If such reactions would occur, it might manifest with fever, chills, rigors, headache, rash, pruritus, arthralgias, hypotension, hypertension, bronchospasm, or other allergic-like reactions. All Grade ≥ 3 infusion reactions should be reported within 24 hours to the Sponsor via the Medical Monitor and be reported as an SAE if it meets the criteria. Infusion reactions should be graded according to NCI-CTCAE v5.0.

Treatment recommendations are provided below and may be modified based on local treatment standards and guidelines, as appropriate:

- For Grade 1 symptoms: (mild reaction; infusion interruption not indicated; intervention not indicated):
 - Remain at bedside and monitor patient until recovery from symptoms. The following prophylactic pre-medications are recommended for future infusions; diphenhydramine 50 mg (or equivalent), and/or acetaminophen 325 to 1000 mg orally at least 30 minutes before additional administrations.
- For Grade 2 symptoms: (moderate reaction requires therapy or infusion interruption but responds promptly to symptomatic treatment [e.g. antihistamines, nonsteroidal anti-inflammatory drugs, narcotics, corticosteroids, bronchodilators, IV fluids]; prophylactic medications indicated for ≤ 24 hours):
 - Stop the infusion, begin an IV infusion of normal saline, and treat the patient with diphenhydramine 50 mg IV (or equivalent), and/or acetaminophen 325 to 1000 mg PO; remain at bedside and monitor patient until resolution of symptoms. Corticosteroid and/or bronchodilator therapy may also be administered as appropriate. If the infusion is interrupted, then restart the infusion at 50% of the original infusion rate when symptoms resolve; if no further complications ensue after 30 minutes, the rate may be increased to 100% of the original infusion rate. Monitor patient closely. If symptoms recur, then no further drug will be administered at that visit.
 - For future infusions, the following prophylactic pre-medications are recommended: diphenhydramine 50 mg (or equivalent), and/or acetaminophen/paracetamol 325 to 1000 mg PO administered at least 30 minutes before infusions. If necessary, corticosteroids (up to 25 mg IV of hydrocortisone or equivalent) may be used.

- For Grade 3 or 4 symptoms: (severe reaction, Grade 3: prolonged [i.e. not rapidly responsive to symptomatic medication and/or brief interruption of infusion]; recurrence of symptoms following initial improvement; hospitalization indicated for other clinical sequelae [e.g. renal impairment, pulmonary infiltrates]. Grade 4: life-threatening; pressor or ventilatory support indicated):
 - Immediately discontinue infusion of the compound. Begin an IV infusion of normal saline and treat the patient as follows: recommend bronchodilators, epinephrine 0.2 to 1 mg of a 1:1000 solution for subcutaneous administration or 0.1 to 0.25 mg of a 1:10 000 solution injected slowly for IV administration, and/or diphenhydramine 50 mg IV with methylprednisolone 100 mg IV (or equivalent), as needed. The patient should be monitored until the Investigator is comfortable that the symptoms will not recur. Investigators should follow their institutional guidelines for the treatment of anaphylaxis. Remain at bedside and monitor patient until recovery of the symptoms. Further treatment of the patient should be held, and assessments made per the general and specific safety rules of the trial.

Late-occurring hypersensitivity symptoms

In case of late-occurring hypersensitivity symptoms (e.g. appearance of a localized or generalized pruritus within 1 week after treatment), symptomatic treatment may be given (e.g. oral antihistamine or corticosteroids).

12.5 Appendix 5: Management algorithms regarding nivolumab for studies under CTCAE version 5.0

These general guidelines are standard nivolumab protocol safety algorithms (28-Sep-2020) and recommended for inclusion in any nivolumab containing protocol by Bristol-Myers Squibb (marketing authorization holder for nivolumab).

These general guidelines constitute guidance to the Investigator and may be supplemented by discussions with the Medical Monitor representing the Sponsor. The guidance applies to all immuno-oncology agents and regimens.

A general principle is that differential diagnoses should be diligently evaluated according to standard medical practice. Non-inflammatory etiologies should be considered and appropriately treated.

[figure not shown]
Corticosteroids are a primary therapy for immuno-oncology drug-related adverse events. The oral equivalent of the recommended IV doses may be considered for ambulatory patients with low-grade toxicity. The lower bioavailability of oral corticosteroids should be taken into account when switching to the equivalent dose of oral corticosteroids.

Consultation with a medical or surgical specialist, especially prior to an invasive diagnostic or procedure, is recommended.

The frequency and severity of the related adverse events covered by these algorithms will depend on the immuno-oncology agent or regimen being used.

GI Adverse Event Management Algorithm

Rule out non-inflammatory causes. If non-inflammatory cause is identified, treat accordingly and continue I-O therapy.
 Opiates/narcotics may mask symptoms of perforation. Infliximab should not be used in cases of perforation or sepsis.

[figure not shown]

Patients on IV steroids may be switched to an equivalent dose of oral corticosteroids (eg, prednisone) at start of tapering or earlier, after sustained clinical improvement is observed. Lower bioavailability of oral corticosteroids should be taken into account when switching to the equivalent dose of oral corticosteroids.

* Discontinue for Grade 4 diarrhea or colitis. For Grade 3 diarrhea or colitis, 1) Nivolumab monotherapy: Nivolumab can be delayed. 2) Nivolumab+ Ipilimumab combination: Ipilimumab should be discontinued while nivolumab can be delayed. Nivolumab monotherapy can be resumed when symptoms improve to Grade 1. Please refer to protocol for dose delay and discontinue criteria for other combinations.

Renal Adverse Event Management Algorithm

[figure not shown]
Rule out non-inflammatory causes. If non-inflammatory cause, treat accordingly and continue I-O therapy.

Patients on IV steroids may be switched to an equivalent dose of oral corticosteroids (eg, prednisone) at start of tapering or earlier, after sustained clinical improvement is observed. Lower bioavailability of oral corticosteroids should be taken into account when switching to the equivalent dose of oral corticosteroids.

Pulmonary Adverse Event Management Algorithm

[figure not shown]
Rule out non-inflammatory causes. If non-inflammatory cause, treat accordingly and continue I-O therapy.
Evaluate with imaging and pulmonary consultation.

Patients on IV steroids may be switched to an equivalent dose of oral corticosteroids (eg, prednisone) at start of tapering or earlier, after sustained clinical improvement is observed. Lower bioavailability of oral corticosteroids should be taken into account when switching to the equivalent dose of oral corticosteroids.

Hepatic Adverse Event Management Algorithm

Rule out non-inflammatory causes. If non-inflammatory cause, treat accordingly and continue I-O therapy.
Consider imaging for obstruction.

[figure not shown]
Patients on IV steroids may be switched to an equivalent dose of oral corticosteroids (e.g. prednisone) at start of tapering or earlier, after sustained clinical improvement is observed. Lower bioavailability of oral corticosteroids should be taken into account when switching to the equivalent dose of oral corticosteroids.

[^] Please refer to protocol dose delay and discontinue criteria for specific details.

*The recommended starting dose for AST or ALT > 20 x ULN or bilirubin >10 x ULN is 2 mg/kg/day methylprednisolone IV.

Endocrinopathy Adverse Event Management Algorithm

Rule out non-inflammatory causes. If non-inflammatory cause, treat accordingly and continue I-O therapy.
Consider visual field testing, endocrinology consultation, and imaging.

[figure not shown]
Patients on IV steroids may be switched to an equivalent dose of oral corticosteroids (eg, prednisone) at start of tapering or earlier, after sustained clinical improvement is observed. Lower bioavailability of oral corticosteroids should be taken into account when switching to the equivalent dose of oral corticosteroids.

NOTE, below guidance is for nivolumab given as monotherapy! EO2401

DO NOT FOLLOW THE BELOW GUIDANCE FOR ADMINISTRATION SITE REACTIONS RELATED TO EO2040; CONTACT THE MEDICAL MONITOR IN ANY CASE OF DOUBT OF HOW SUCH REACTIONS SHOULD BE HANDLED!

Skin Adverse Event Management Algorithm

Rule out non-inflammatory causes. If non-inflammatory cause, treat accordingly and continue I-O therapy.

[figure not shown]
Patients on IV steroids may be switched to an equivalent dose of oral corticosteroids (e.g. prednisone) at start of tapering or earlier, after sustained clinical improvement is observed. Lower bioavailability of oral corticosteroids should be taken into account when switching to the equivalent dose of oral corticosteroids.

*Refer to NCI CTCAE v5 for term-specific grading criteria.

^If Steven-Johnson Syndrome (SJS), toxic epidermal necrosis (TEN), Drug Reaction with Eosinophilia and Systemic Symptoms (DRESS) is suspected, withhold I-O therapy and refer patient for specialized care for assessment and treatment. If SJS, TEN, or DRESS is diagnosed, permanently discontinue I-O therapy.

Neurological Adverse Event Management Algorithm

Rule out non-inflammatory causes. If non-inflammatory cause, treat accordingly and continue I-O therapy.

[figure not shown]

Patients on IV steroids may be switched to an equivalent dose of oral corticosteroids (eg. prednisone) at start of tapering or earlier, after sustained clinical improvement is observed. Lower bioavailability of oral corticosteroids should be taken into account when switching to the equivalent dose of oral corticosteroids.

[^]Discontinue for any grade myasthenia gravis, Guillain-Barre syndrome, treatment-related myelitis, or encephalitis.

Myocarditis Adverse Event Management Algorithm

Rule out non-inflammatory causes. If non-inflammatory cause, treat accordingly and continue I-O therapy.

Patients on IV steroids may be switched to an equivalent dose of oral corticosteroids (eg, prednisone) at start of tapering or earlier, after sustained clinical improvement is observed. Lower bioavailability of oral corticosteroids should be taken into account when switching to the equivalent dose of oral corticosteroids. Prophylactic antibiotics should be considered in the setting of ongoing immunosuppression.

1 DOCUMENT HISTORY

Version	Date	Author / editor of new version	Main changes / comments
v01	06-Mar-2024	[REDACTED]	First version

2 LIST OF ABBREVIATIONS

Abbreviation	Text
AE	Adverse Events
APS	All-Patient Set
ATC	Anatomical Therapeutic Chemical
BIRC5	Baculoviral Inhibitor of Apoptosis Repeat-containing5
CRC	Colorectal cancer
CRF	Case Report Form
CSR	Clinical Study Report
ctDNA	Circulating tumor deoxyribonucleic acid
DFS	Disease-free survival
DNA	Deoxyribonucleic acid
eCRF	Electronic Case Report Form
ELISpot	Enzyme-linked Immunospot
FAS	Full Analysis Set
FOXM1	forkheadboxM1
ICH	International Council for Harmonization
IFN- γ	Interferon-gamma
IHC	Immunohistochemistry
MDSC	Myeloid-derived suppressor cells
MedDRA	Medical Dictionary for Regulatory Activities
MRD	Minimal residual disease
NCI-CTCAE	National Cancer Institute-Common Terminology Criteria for AE
OS	Overall Survival
PD-L1	Programmed Death-Ligand 1
PPS	Per-Protocol Set
PT	Preferred Term
QC	Quality control
SAE	Serious Adverse Event
SOC	Standard of Care, System Organ Class
SOP	Standard Operating Procedure
SS	Safety Set
TAA	Tumor associated antigens
TCR	T cell Receptor
TEAE	Treatment-Emergent Adverse Events
UCP2	Universal Cancer Peptide 2
WHODD	World Health Organization Drug Dictionary

3 GENERAL

This statistical analysis plan reflects study protocol EOCRC1-22 dated 04-JUL-2022. It follows the principles of the Guidelines International Council for Harmonization (ICH) Topic E3 and ICH Topic E9. It gives all details for the final statistical analysis of this study.

3.1 Analyses Planned and Already Performed

No formal analysis of the data will be performed as the study is planned to be terminated with just one treated patient, only patient data listings will be produced.

3.2 SOPs to be Followed

The analysis will be carried out according to Metronomia Standard Operation Procedures (SOPs).

The report will be written according to the ICH E3 and other applicable ICH guidelines.

4 OVERVIEW OF THE PROTOCOL

4.1 Study Objectives

4.1.1 Primary Objective

- The primary objective of this trial is to assess the 6-month circulating tumor deoxyribonucleic acid (ctDNA) clearance rate at therapy with EO2040 in combination with nivolumab, in patients with ctDNA-defined minimal residual disease (MRD) of stage II-IV colorectal cancer after completion of curative therapy.

and in sequence, provided the first objective has a positive outcome per protocol

Section 9:

- The primary objective is, to assess the 6-month ctDNA clearance rate at therapy with EO2040 monotherapy, in patients with ctDNA-defined MRD of stage II-IV colorectal cancer after completion of curative therapy.
 - In case the first objective does not have a positive outcome per protocol Section 9, a protocol amendment to adjust the second part of the primary objective to utilize an alternative therapeutic vaccine than EO2040 will be considered.*

ctDNA clearance is utilized as a surrogate endpoint for eventual cure, and thereby prolongation of disease-free survival (DFS) for patients achieving clearance.

Note, clearance of ctDNA is characterized by the disappearance of all somatic mutations identified in the blood, as well as no appearance of any additional new somatic mutations, and radiographic investigation(s) showing no evidence of colorectal cancer (see protocol Section 7.8).

4.1.2 Secondary Objectives

To assess the following items at therapy with EO2040 in combination with nivolumab, and when applicable EO2040 monotherapy, in patients with ctDNA-defined MRD of stage II-IV colorectal cancer after completion of curative therapy:

- Safety and tolerability of study treatments,
- The 3-month ctDNA clearance rate,

- Progression of colorectal cancer and death as DFS,
- Overall Survival (OS),
- Survival at 36 months after start of study therapy, and
- Induction/expansion of T cells specific for EO2040, the components of EO2040, and the targeted nominal tumor associated antigens (TAAs) (Baculoviral Inhibitor of Apoptosis Repeat-containing5 [BIRC5] and forkheadboxM1 [FOXM1]).

4.1.3 Exploratory Objectives

- To assess correlations between immunogenicity of EO2040, the components of EO2040, and the targeted nominal TAAs (BIRC5 and FOXM1) and efficacy, and safety, outcome parameters.

4.2 Study Endpoints

4.2.1 Primary Endpoint

- The primary endpoint is response to treatment at 6 months (see protocol Section 3.1.1), which is defined as having clearance of ctDNA, AND not having any radiographic evidence of recurrence at 6 months (see also protocol Section 7.8 for rules of assessment of an individual patient best overall response).

Clearance of ctDNA will be characterized by the disappearance of all somatic mutations

identified in the blood, as well as no appearance of any additional new somatic mutations.

4.2.2 Secondary Endpoint

- The safety and tolerability of study treatments will be determined by a descriptive medical assessment of the combined profile of incidences of adverse events (AEs), treatment-emergent AEs (TEAEs), serious AEs (SAEs), deaths, reasons for treatment discontinuation/delays, and laboratory abnormalities using the NCI-CTCAE v5.0 grading system (see Section 11.3 below and Section 7.7 in protocol).
- Response to therapy at 3 months, defined as clearance of ctDNA, AND no radiographic evidence of recurrence (determination method will be the same as for the primary endpoint; see protocol Section 3.2.1).
- DFS defined as the time from start of study treatment to the date of first documented CRC recurrence or death due to any cause, whichever occurs first. Patients alive without recurrence will be censored at the date of last follow-up time. Recurrence is defined by the appearance of one or more new CRC lesions on imaging and/or other clinical evaluation such as endoscopy.
- OS, measured as the time from start of study treatment until death from any cause. Patients alive will be censored at the last time documented to be alive.
- Survival at 36 months after start of study treatment, estimated via Kaplan-Meier estimates.
- Immunogenicity and cross reactivity: immunogenicity determined as expansion of specific T cells comparing samples taken at baseline versus on treatment in an individual patient

[REDACTED]

4.2.3 Exploratory Endpoint

[REDACTED]

- Correlations between immunogenicity [REDACTED]

[REDACTED] of EO2317, EO2318, and UCP2 and clinical efficacy (per primary and secondary efficacy endpoints) and safety (TEAEs of defined specificities and grades) outcome parameters. Cross reactivities shown for the TAAs BIRC5/survivin, and FOXM1 will also be explored in the same way.

- [REDACTED]

4.3 Study Design

[figure not shown]
The trial is a multi-center, open-label, non-comparative, two sequential cohort, phase 2 trial, to investigate as the first cohort efficacy of the microbiome-derived therapeutic vaccine EO2040 in combination with nivolumab in patients with stage II-IV colorectal cancer with ctDNA defined MRD after completion of curative therapy. Assuming a positive outcome of the first cohort, a second cohort assessing efficacy of EO2040 monotherapy, with the option of addition of nivolumab after 3 months in case of no ctDNA clearance, is planned.

The study is assumed to recruit a total of 17 patients in Cohort 1, and if cohort 1 has a positive outcome (see protocol Section 9), a total of 17 patients will also be recruited to Cohort 2A.

Schematic overview of the trial design, and an overview of the treatment schedule are illustrated in figures below.

Trial design overview:

Treatment schedule, scan and ctDNA assessments, and blood sampling for immune testing and serum collection:

[figure not shown]
Statistical Analysis Plan

Version/Status/Date: v01/final/06-Mar-2024

Enterome: EOCRC1-22

(EN05)

[figure not shown]
Page 10 of 16

4.4 Sample Size

Considering prior attempts in similar situations, the trial will include 17 patients per cohort.

The primary objective of the trial is to determine the ctDNA clearance rate at 6 months (R6).

4.5 Study Flow Chart

Refer the latest study protocol.

5 GENERAL ASPECTS OF THE STATISTICAL ANALYSIS

5.1 Analysis Sets

The **All-Patient (AP) set** will consist of any patient who signed informed consent including screen-failures.

The **Full Analysis Set (FAS)** will consist of patients who received at least one dose of EO2040 and for whom no important protocol deviations occurred that would compromise the evaluation of efficacy.

The **Safety Set (SS)** will consist of patients who received at least one dose of study treatment.

[REDACTED]

[REDACTED]

[REDACTED]

5.2 Protocol Deviations

All protocol deviations regardless of their source will be listed for each patient together with the categorization into major or minor.

5.3 Intercurrent Events

Not Applicable.

5.4 Changes or Deviations from Planned Analyses

Since the study is planned to be terminated with just one treated patient, no formal analysis of the data will be performed.

6 DEFINITIONS FOR STATISTICAL ANALYSIS

6.1 Baseline and Change from Baseline

Baseline is defined as the last non-missing value prior to first administration of study treatment.

Absolute Change from Baseline at a visit/timepoint will be calculated as follows:

Result at visit/timepoint – Baseline result;

For assessments taken before and after first administration of study treatment, baseline assessments will be flagged separately in the listings. Similarly, change from baseline values will be displayed alongside observed results in the respective listings.

6.2 Study Day

The reference day (Day 1) for study day calculations is the date of the first administration (V1) of study treatment. The study day will be calculated as follows:

- Assessment/Visit Date – Date of first administration study treatment + 1; for assessments on or after the date of first administration of study treatment
- Assessment/Visit Date – Date of first administration study treatment; for assessments before the date of first administration of study treatment

There is no Study Day 0.

Study day will be displayed alongside visit/event dates in the relevant listings.

6.3 Duration

Duration of an event will be calculated as follows:

Duration (days) = (End date of event – Start date of event) +1;

[figure not shown]
In case of partial start/end dates, duration will be calculated assuming the 15th of the respective months if case of missing day. Duration will not be calculated if months and day are not given.

All listings displaying event data like AE, medication, etc., will include duration of the events alongside the end dates.

6.4 Visit windows and Analysis Visits

Data collected by visit will be displayed for the visit it was collected, irrespective of the actual date of the assessment.

The following tables shows the visit labels to be used in patient data listings:

7 STATISTICAL ANALYSIS SPECIFICATION

7.1 Specifications Related to Whole Analysis

7.1.1 Tables

No tables will be produced.

7.1.2 Data Listings

All CRF data will be listed as documented. For screen failures only demographic data and screen failure details will be listed. Relevant generated variables from section 6 will be listed

next to the original data items as well.

In all listings, the cohort labels will be displayed as given below:

- Cohort 1
- Cohort 2A
- Cohort 2B

In listings with screen failure data, screen failures will have cohort label as “Not Applicable” and will be sorted at last.

The listings will be sorted by cohort, patient identifier, visit and date (if applicable).

Medical history, Procedures and Adverse event:

All medical history, concomitant illness, procedures and adverse events will be coded using MedDRA version mentioned in the latest data management plan and system organ class (SOC), preferred term (PT) of the events will be presented in the listing.

Medication:

All medication will be coded using World Health Organization Drug Dictionary (WHODD) version mentioned in the latest data management plan and Anatomical Therapeutic Chemical (ATC) level 2 term, PT of the medications will be presented in the listing.

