5.3.2 Screen failures

Screen failures are defined as patients who consent to participate in the clinical study but are not subsequently treated with study drug(s) due to failure of the eligibility criteria. [REDACTED]

[REDACTED]

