8.3 Safety monitoring periods

8.3.1 Reporting

In patients exposed to study treatment, the following must be reported from the date of the patient's signing the ICF until 30 days after the final administration of study treatment:

- AEs regardless of their causal relationship to study treatment,
- SAEs without a plausible causal relationship to study treatment, and
- pregnancy of the patient or the patient's sexual partner.

SAEs with a plausible causal relationship to study treatment must be reported from the date of the patient's signing the ICF until indefinitely (regardless of the time elapsed from the final study treatment administration).

In patients not exposed to study treatment, the reporting period for AEs (including SAEs regardless of causal relationship) starts with signature of the ICF and ends:

- the date of the Investigators assessment of "screen failure"-status (see [Section 5.3.2](#)), or
- the date of the patient's consent withdrawal.

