8.5 Reporting by the investigational site

8.5.1 Adverse events

Any AE (including SAEs), whether, or not considered to be causally related to the trial medication and regardless of its seriousness, must be described and recorded in the AE section of the patient's eCRF on an ongoing basis.

A pre-existing condition is a clinical condition (including a condition being treated) that is diagnosed before the patient signs the ICF and that is documented as part of the patient's medical history; any clinically significant worsening of a pre-existing condition constitutes an AE. Also, any recurrence of a pre-existing condition is an AE.

The questions concerning whether the condition existed before the start of the active phase of the study and whether it has increased in severity and/or frequency will be used to determine whether an event is a TEAE. An AE is considered to be treatment-emergent if it is not present when the active phase of the study begins and is not a chronic condition that is part of the patient's medical history, or it is present at the start of the active phase of the study or as part of the patient's medical history, but the severity or frequency increases during the active phase. The active phase of the study begins at the time of the first dose of the study drug. The active phase of the study ends at the post-treatment visit for safety assessment (see **Table 8**).

A standardized question such as "Have you had any health problems since your last visit or since you were last questioned?" will be given by the Investigator or the investigational site personnel at each contact with the patient.

Progression of the underlying disease or an AE unequivocally (without doubt) related to the progression of the underlying disease, regardless of its outcome or seriousness criteria, does not need to be reported as an AE/SAE. However, the medical conditions and underlying diseases associated with disease progression needs to be captured on the AE eCRF page (as a non-serious AE). An SAE must be reported only if there are clinical symptoms/signs that cannot be without doubt associated with the progression of the underlying disease.

Whenever possible, a diagnosis rather than symptoms should be provided (e.g. anemia instead of low Hb).

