9 STATISTICAL EVALUATION

9.1 Analysis populations

The All-Patient (AP) population will consist of any patient who signed informed consent including screen-failures.

The Full Analysis Set (FAS) will consist of patients who received at least one dose of EO2040 and for whom no important protocol deviations occurred that would compromise the evaluation of efficacy.

The Safety Set (SS) will consist of patients who received at least one dose of study treatment.

[REDACTED]

Efficacy will be analyzed using both the FAS and PP populations. Safety will be analyzed using the SS, however applicable adverse events for the AP population will be reported in by-patient listings (e.g. events during screening).

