9.2 Statistical methods

All data collected in this trial will be reported by patient data listings, summary tables, and figures for all demographic and baseline characteristics, medical history, efficacy, and safety variables. Proportions and the denominators will be provided to summarize response, toxicity, and other categorical variables.

[REDACTED]

Statistical assessments of correlations between e.g. immunogenicity parameters (see [Section 3.2.3](#), and [Section 7.9](#)) and efficacy and safety outcome parameters will be conducted as described in the Statistical Analysis Plan (SAP).

The SAP will provide all details with respect to patients being analyzed for all endpoints. Relevant subgroups based on available data and compliance to protocol procedures might be defined.

Statistical tests may be planned in the SAP or performed as needed. The importance of the tests does not reside in making conclusions on statistical relevance of differences, but rather identification of possible results that could be worth further exploration.

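### Minor: the SAP leaves adverse events of screen failures out of the listings the Protocol assigns them to, and its 15th-of-month rule can give durations of 0 or less

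*SAP*

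**What the plan says.** **Screen failures.** Protocol 9.1 analyses safety on the Safety Set, then adds that "applicable adverse events for the AP population will be reported in by-patient listings (e.g. events during screening"). It defines the AP population as everyone who signed consent, screen failures included. SAP 5.1 keeps that definition: the AP set "will consist of any patient who signed informed consent including screen-failures". SAP 7.1.2 begins by listing all CRF data as documented, then makes an exception: "For screen failures only demographic data and screen failure details will be listed". SAP 5.4, the section for departures from the planned analyses, records only that "no formal analysis of the data will be performed" because the study is to stop with one treated patient.

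**Duration.** SAP 6.3 defines duration as end date minus start date plus 1. When the day is missing it uses the 15th of that month; when day and month are both missing it calculates nothing. It prints durations in every listing of event data. It states no check that an imputed date is consistent with the known one.

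**The concern.** The Protocol extends adverse event listings from treated patients to all who consented. The patients this adds are the untreated ones, mainly screen failures. The SAP's restriction drops all of their events, so it removes most of what the Protocol clause provides.

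Early termination does not explain this. It removed formal analysis, tables and figures but kept the listings (SAP 3.1, 7.1.1, 11.1). Because listings are the only output, an event left out of them is left out of everything the SAP produces.

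The duration rule raises a smaller problem. Followed literally, it can print a zero or negative length for an event. Only a derived value shown beside the recorded dates is affected.

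**Working it through.** **Part (a): comparison of the texts**

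1. *Who is in the AP population?* Everyone who consented, screen failures included (Protocol 9.1, SAP 5.1).
2. *Are their adverse events collected?* For patients not exposed to treatment, "the reporting period for AEs (including SAEs regardless of causal relationship) starts with signature of the ICF" and ends at the screen-failure assessment or withdrawal of consent (Protocol 8.3.1). Protocol 8.5.1 requires that any adverse event, "regardless of its seriousness, must be described and recorded in the AE section of the" eCRF. Protocol 10.7 requires an eCRF for each patient who signs consent and undergoes any screening procedure. The eCRF completion instructions are not visible, so what is actually held is an assumption.
3. *Are screen failures to be expected?* Yes. Protocol 4.2 expects about half of the patients not to match HLA-A2. For those who fail at this first stage, Protocol 7.3 is unclear on when recording starts: it begins adverse event documentation after the initial consent but ties consent-related timelines to the second consent.
4. *What does the SAP list for them?* Demographics and screen-failure details, with the word *only*. On the visible wording, none of their adverse events are listed.
5. *Is the departure declared?* SAP 5.4 does not mention it.

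**Part (b): date arithmetic**

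Input: duration = end − start + 1, with a missing day set to 15 (SAP 6.3). The formula is right for complete dates: 1 March to 10 March gives 10 days.

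Both dates in the same month, exactly one day missing:

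| Missing | Formula | 0 or less when | Range of those values | Example |
|---|---|---|---|---|
| End day | 15 − s + 1 = 16 − s | start day s is 16 or later | 0 (s = 16) down to −15 (s = 31) | 28 March to March: 16 − 28 = −12 |
| Start day | e − 15 + 1 = e − 14 | end day e is 14 or earlier | 0 (e = 14) down to −13 (e = 1) | March to 5 March: 5 − 14 = −9 |

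In a 31-day month that is 16 of 31 possible start days and 14 of 31 possible end days.

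The problem does not arise elsewhere:

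- Both days missing in one month: 15 − 15 + 1 = 1.
- Adjacent months, end day missing: the minimum is 16, from a start on the last day of the earlier month.
- Adjacent months, start day missing: the minimum is 15, from 15 February to 1 March in a non-leap year.
- Adjacent months, both days missing: the minimum is 29, from 15 February to 15 March in a non-leap year.

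The adjacent-month minima come from running every date of 2022, 2023 and 2024.

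**The case against.** *On (a).* The Protocol promises only *applicable* events and does not define the word. Treated patients also belong to the AP population, and their pre-dose events are listed under the general rule of SAP 7.1.2, so the Protocol's example of events during screening is met for the one treated patient. Protocol 9.2 also delegates: "The SAP will provide all details with respect to patients being analyzed for all endpoints". The restriction is openly stated in SAP 7.1.2. Text is redacted in Protocol 5.3.2, Protocol 9.1 and SAP 5.1, and the listing index in SAP 11.2 is not visible.

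Some of this stands. There is discretion, and the missing text could bear on the point. But the AP definition names screen failures, and a rule excluding every one of their events goes beyond choosing which are applicable. Protocol 9.2 also opens by committing all collected data, safety variables included, to listings, tables and figures. An index that did list these events would contradict SAP 7.1.2.

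*On (b).* The reader sees the recorded dates beside the derived value, no summary uses duration, data queries may resolve partial dates, and SAP 8 refers to programming procedures and a quality-control plan that are not visible. All of that limits the harm. It does not change what SAP 6.3 yields as written, and nothing visible corrects it.

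**Conclusion.** Both points hold, and both are minor.

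(a) The visible wording of SAP 7.1.2 conflicts with Protocol 9.1, and the difference is undeclared. This is a reporting mismatch: no estimate, test or decision depends on it, and serious events are still reported through Protocol 8.5.3. The documents give neither the number of screen failures nor whether any had an adverse event, so the number of omitted events is unknown and may be zero. The conclusion assumes that no redacted text, and nothing in the unseen listing index, reconciles the two sections.

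(b) SAP 6.3 can give durations from 0 down to −15 (end day missing) or 0 down to −13 (start day missing), only when exactly one day is missing and both dates share a month. The documents give no frequency of partial dates, so no rate is claimed for this trial.

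**What to change.** - **SAP 7.1.2:** for screen failures, list demographics, screen-failure details and any adverse events, serious or not, recorded for them. Leave study day blank, because SAP 6.2 counts it from first administration. If the omission is intended, declare and justify it in SAP 5.4 instead.
- **SAP 6.3:** leave duration blank when the imputed date would put the end before the start. A duration of 0 or less is the same condition as end before start, so this catches every case.

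The cost is one sentence in each place and one programming condition. SAP 7.1.2 already has a cohort label and a sort rule for screen failures. The downside is a slightly longer adverse event listing and a few blank durations.
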